2.7.2.3 Parasite clearance time (PCT) and fever clearance time (FCT)

Descriptive statistics (mean, standard error, median, quartiles) will be presented using the Kaplan-Meier method. Kaplan-Meier curves will be provided.

PCT will be calculated based on uncorrected asexual parasite counts. Patients without parasite clearance for whatever reason will be censored at the time of last parasite assessment. Patients who were enrolled on the basis of history of fever and did not subsequently have a fever at pre-dose will not be included in the analysis of FCT. Patients without fever clearance for whatever reason will be censored at the time of last temperature assessment. Patients who received any antimalarial medication (including rescue medication) before (parasite or fever) clearance will be censored at the first use of antimalarial medication. The difference between each test group and control will be evaluated using a log-rank test. Patients who did not experience a clearance will be censored at the time of last relevant assessment (parasite or fever). For the pooled analysis, the log-rank test will be stratified by Part.

2.7.2.4 Time to event analysis for Recrudescence

Recrudescence is defined as appearance of asexual parasites after clearance of initial infection with a genotype identical to that of parasites present at baseline. Recrudescence must be confirmed by PCR analysis.

Incidence rates of recrudescence at Days 15, 29 and 43 will be estimated by the Kaplan-Meier method based on the subset of FAS patients who have clearance of initial infection before Day 15.

Time to event (recrudescence) will be calculated from the time of first study medication to the date of first event if a patient experience the event and be censored at the time of last parasite assessment if a patient does not experience the event. Undertermined treatment failures due to missing PCR data will be considered as censored at the time of treatment failure.

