#### **Late Parasitological Failure (LPF)**

- Presence of parasitaemia on any day from Day 8 to Day 43 and axillary temperature  $< 37.5^{\circ}\text{C}$  without previously meeting any of the criteria of Early Treatment Failure or Late Clinical Failure

Commencement of rescue medication with a combination antimalarial product (local standard at the discretion of the investigator or a medically qualified person) may occur after start of trial medications and up to 43 days after the last dose of KAF156/LUM-SDF as deemed necessary by the investigator. Lumefantrine-based treatment must be avoided in case of early treatment failure (ETF). Patients will be monitored, either in clinic, by telephone, or via home visits for three days to ensure adherence to the rescue medication therapy. These patients will not be replaced and will not discontinue the study (i.e., all the examinations as per the assessment schedule and all CRF pages for this patient will need to be completed).

Safety blood tests (Full Blood Count (FBC) and Blood chemistry) will be collected on the initial day of rescue medication dosing. Blood films and blood sampling for parasite count and genotyping must be taken before giving the established anti-malarial treatment.

Patients treated with at least one dose of trial medications will continue to be followed-up until Day 43 according to schedule.

Use of rescue medication (including exact rescue regimen and route of administration) must be recorded on the Concomitant medications/Significant non-drug therapies after start of study drug.

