 Laboratory tests should also be taken at any time of withdrawal/discontinuation. [REDACTED]

 The patient's menstrual and contraceptive history will be taken and a urine  $\beta$ -hCG pregnancy test will be performed at screening to exclude pregnancy and at end of study. Results must confirm negative before dosing.

 Pre-screening parasite count should be used as baseline count. In case parasite count has been done > 6 hours before Study Visit 99 then it should be repeated at Study Visit 99 and the outcome of the repeated test should be considered as baseline parasite count

 PCR will be used for genotyping to establish malaria recrudescence/reinfection. PCR blood samples will be used for reviewing resistance markers. At screening, blood sample will be collected in all patients fulfilling eligibility criteria for inclusion in the study. A second blood sample collected as per Table above will be analyzed only in patients showing treatment failure before standard-of-care is administered.

[REDACTED]

 Meals within 3 hours prior to dosing and within 4 hours post-dosing to be documented.

 IRT has to be notified at Study Visit 1, at each study drug dispensing and at the completion or discontinuation of study treatment, upon completion of study or premature withdrawal from study participation. Also, if a patient vomits study drugs and needs to take a replacement medication, the site staff need to notify IRT.

[REDACTED]

 Screen Epoch has 2 parts: a Pre-Screening Part (Study Visit 1) to successfully identify the correct patients to be screened for this clinical study, and a Screening Part (Study Visit 99) in which further assessments will take place.

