2.5.4.1 Analysis of PCR-corrected ACPR rate using Kaplan-Meier method

For the FAS, the proportion of patients with PCR-corrected ACPR at Day 29 and 95% CI will be also estimated using the Kaplan-Meier method ([Stepniewska and White 2006](#) and [WHO 2015](#))

Event = PCR-corrected non-responder during the study (same as at Day 15, Day 43, See Section 2.1). The event time is the first time when the patient becomes a non-responder based on PCR-correction. If a patient parasite is not cleared at all, Day 7 is considered as the event time.

The PCR-corrected responder rate at Day 29 is estimated by the survivor function at Day 29 using the Kaplan-Meier method.

Rule for censoring:

The following censoring rules will be applied to the patients who were not non-responder

- Patients who had a new infection (i.e., reinfection) with *P. falciparum* or other species without *P. falciparum* recrudescence on or after Day 8 will be censored at the first time of the PCR that indicate the infection or blood smear with other species;
- Patients who received non-rescue antimalaria medication for other infections, such as *P. falciparum* gametocytes, will be censored at the first time of antimalaria medication;
- Patients who have parasites at Day 8 or later but cannot be determined as recrudescence or new infection due to missing PCR genotyping will be censored at the time of the first malaria blood film with presence of parasites on or after Day 8.
- other patients not classified as non-responder will be censored at the time of last parasitemia assessment.

A two-sided 95% CI for the difference in proportion of responders between each KAF156/LUM-SDF combination treatment group and Coartem[®] will be calculated based on the variance of individual proportion using the Greenwood formula.

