2.7.2.5 Time to event analysis for reinfection

Reinfection is defined as appearance of asexual parasites after clearance of initial infection with a genotype different from those parasites present at baseline. Reinfection must be confirmed by PCR analysis.

Incidence rates of reinfection at Days 15, 29 and 43 will be estimated by the Kaplan-Meier method based on the subset of FAS patients who have clearance of initial infection before Day 15.

Time to event (reinfection) will be calculated from the time of first study medication to the date of first event if a patient experiences the event and be censored at the time of last parasite assessment if a patient does not experience the event. Indetermine treatment failures due to missing PCR data will be considered as censored at the time of treatment failure.

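### The recrudescence and reinfection Kaplan-Meier analyses keep patients at risk after rescue and after the other type of recurrence, in conflict with the SAP's other censoring rules and with no stated target

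*SAP*

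**What the plan says.** SAP 2.7.2.4 estimates the incidence of recrudescence at Days 15, 29 and 43 by Kaplan-Meier, and 2.7.2.5 does the same for reinfection. Both use the "subset of FAS patients who have clearance of initial infection before Day 15". In both, a patient is to "be censored at the time of last parasite assessment if a patient does not experience the event". The only earlier censoring concerns failures without a genotype: "Undertermined treatment failures due to missing PCR data will be considered as censored at the time of treatment failure". Protocol 9.5.1.4 has the same last-assessment rule, with a risk set cleared by Day 7.

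Protocol 5.6.6 keeps rescued patients under observation: "These patients will not be replaced and will not discontinue the study", and "Patients treated with at least one dose of trial medications will continue to be followed-up until Day 43 according to schedule". A footnote to the assessment schedule (Protocol section 6) says the second genotyping sample "will be analyzed only in patients showing treatment failure before standard-of-care is administered".

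Other time-to-event analyses in the SAP end follow-up sooner. Section 2.5.4.1 (Kaplan-Meier for PCR-corrected ACPR) censors at a new infection, and also censors this group at the first such drug: "Patients who received non-rescue antimalaria medication for other infections". Section 2.7.2.3 (clearance times) goes further: "Patients who received any antimalarial medication (including rescue medication) before (parasite or fever) clearance will be censored at the first use of antimalarial medication".

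**The concern.** Three kinds of patient carry event-free time that does not reflect the study drug alone.

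- A patient with a PCR-confirmed new infection at Day 15 who is then given another antimalarial stays at risk of recrudescence to Day 43.
- A patient who recrudesces and is rescued stays at risk of reinfection while covered by the rescue drug.
- An early failure rescued on Day 4 who then clears can satisfy the clearance condition and enter both risk sets.

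The rule is also inconsistent with itself. A Day 15 failure with missing PCR is censored at Day 15. The same patient with a PCR result showing new infection stays at risk of recrudescence to Day 43.

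Incidence of recrudescence and reinfection is a listed secondary endpoint in a dose-selection trial. If its target is undefined, the reported rate has no clear meaning and cannot be read alongside the Kaplan-Meier ACPR curve.

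**Working it through.** The documents give no expected recrudescence, reinfection or rescue rate, so there is no figure of the plan's own to reproduce here. All recurrence rates below are assumptions. The arm size of 50 is the number randomized per KAF156 arm (42/0.84 = 50).

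**Hand example (assumed counts).** Take 50 cleared patients, with 5 new infections rescued at Day 15 and 10 at Day 29, and recrudescence in 3 at Day 29 and 2 at Day 43.

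- As written, the patients with new infections stay in the denominator. Day 29: 3/50 = 6.0%. Day 43: 1 − (47/50)(45/47) = 10.0%.
- Censored at new infection or rescue, 50 − 5 = 45 are at risk at Day 29 and 45 − 3 − 10 = 32 at Day 43. Day 29: 3/45 = 6.7%. Day 43: 1 − (42/45)(30/32) = 12.5%.

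The 10.0% is also the crude proportion 5/50, that is, the observed cumulative incidence.

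**Expected values.** Let a and b be the assumed interval probabilities of recrudescence and reinfection among patients with no earlier recurrence, for the visits at Days 15, 29 and 43. Recrudescence takes precedence if both could occur. With A the share still recurrence-free, each interval yields A·a recrudescences and A·(1 − a)·b reinfections. As written, with no post-rescue events, the Day 43 rate is the sum of these. Under censoring it is 1 − Π(1 − a) for recrudescence and 1 − Π(1 − (1 − a)b) for reinfection.

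The assumed probabilities are:

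- recrudescence: low 1/3/1%, high 8/15/5%, very high 15/25/10%;
- reinfection: low 1/5/5%, high 5/15/20%.

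Worked case, very high recrudescence with high reinfection:

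- As written, recrudescence is 0.150 + 0.2019 + 0.0515 = 40.3%, and reinfection is 0.0425 + 0.0908 + 0.0927 = 22.6%.
- Censored, recrudescence is 1 − 0.85 × 0.75 × 0.90 = 42.6%, and reinfection is 1 − 0.9575 × 0.8875 × 0.82 = 30.3%.

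Day 43, as written against censored, with no early-failure rescue:

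| Recrudescence / reinfection | Recrudescence | Gap | Reinfection | Gap |
|---|---|---|---|---|
| low / low | 4.8% vs 4.9% | 0.1 | 10.2% vs 10.5% | 0.3 |
| low / high | 4.6% vs 4.9% | 0.3 | 34.0% vs 34.9% | 0.9 |
| high / low | 25.3% vs 25.7% | 0.4 | 8.3% vs 9.6% | 1.3 |
| high / high | 24.3% vs 25.7% | 1.4 | 27.7% vs 32.6% | 4.9 |
| very high / high | 40.3% vs 42.6% | 2.3 | 22.6% vs 30.3% | 7.7 |

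If 5% of the risk set are early failures who cleared after rescue, the last row becomes 38.3% vs 42.6% (gap 4.3) and 21.5% vs 30.3% (gap 8.8). Without early-failure rescue, the Day 15 values do not differ.

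**Against the other target.** The competing-risk cumulative incidence agrees with the written rule to 0.1 point in every scenario without post-rescue events.

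**If post-rescue reinfections are genotyped and counted** at an unchanged hazard, the high/high reinfection rate is 32.9%, against 32.6% censored and 27.7% cumulative incidence of reinfection as first recurrence. The difference of 32.9 − 27.7 = 5.2 points is made up of events after another drug, charged to the study arm.

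**Total rescue use.** Taking every recurrence as rescued, low/high has 4.6 + 34.0 = 38.6% rescued and gaps of 0.3 and 0.9. High/low has less rescue, 25.3 + 8.3 = 33.6%, but larger gaps of 0.4 and 1.3.

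**The case against.** A reader might infer that both rates are simply understated. The documents do not support that. The endpoint is named only as an incidence rate, and with complete follow-up the written rule returns the observed cumulative incidence. The higher figures answer a different question: the risk had rescue and the other recurrence not intervened. They also assume that patients censored at those points would have had the same later risk as the rest. The direction for reinfection further depends on whether films after rescue are genotyped. The schedule footnote suggests not, but does not settle it.

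A reader might also infer that the shortfall is greatest in the arms with most rescue. The last comparison above contradicts this. Rescue for recrudescence follows that event and cannot dilute its own curve. The recrudescence gap comes from earlier reinfection, early-failure rescue and other antimalarials. The reinfection gap comes from earlier recrudescence, early-failure rescue and other antimalarials.

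Three further points have force.

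- Section 2.5.4.1 has no rule that censors at rescue, and 2.7.2.3 concerns a different endpoint. The recrudescence and ACPR curves would still differ after any fix, because their populations and events differ.
- Clearance of the initial infection is not defined in 2.7.2.4 or 2.7.2.5. If it were taken from the parasite clearance analysis, an early failure censored at rescue would not count as cleared. The SAP does not say so.
- Materiality is limited. An exact 95% interval for 5/50 runs from about 3% to 22%. Section 2.7.2 sets no hypotheses for secondary endpoints, and Table 2-6 marks no between-treatment comparison for these rows. Section 2.15 does not name them among the secondary efficacy measures for the Part A assessment.

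These points limit the size and the direction of the problem. They do not remove the inconsistency: the SAP censors at a missing-PCR failure but not at a PCR-confirmed recurrence of the other type, and it gives no reason.

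**Conclusion.** The concern holds as an inconsistent censoring rule with an unstated target. As Kaplan-Meier estimates of risk under study drug alone, the Day 43 rates are too low when patients who were rescued or had the other recurrence show no later events. The gap is about 0.1 to 2 points for recrudescence and 0.3 to 8 points for reinfection under the assumed rates. It is larger (up to 4.3 and 8.8 points) if 5% of the risk set are rescued early failures, and negligible when recurrences are few. Against observed cumulative incidence there is no understatement, and any genotyped post-rescue events would be charged to the study arm. The conflict between rules rests on the text alone, whereas every magnitude rests on assumed rates. The primary endpoint, its test and the sample size are unaffected.

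**What to change.** In SAP 2.7.2.4 and 2.7.2.5, state the target and apply one of two rules.

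1. For risk under study drug alone, censor at the earliest of the first non-study antimalarial (rescue or other) and the first PCR-confirmed recurrence of the other type. This is in line with the new-infection and non-rescue rules of 2.5.4.1 and the any-antimalarial rule of 2.7.2.3.
2. For observed incidence, say so and use a cumulative incidence function with those occurrences as competing events.

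Under either rule, count a patient as cleared for the risk set only if clearance came before any non-study antimalarial. Declare the departure from protocol 9.5.1.4 in SAP section 4, which now lists no changes.

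The cost is a few sentences and one derived date. The first-antimalarial date is already needed for 2.7.2.3, and no new data are required. Under the first rule, slightly fewer patients are at risk late in follow-up and the rates become slightly less favourable. The SAP's change log already has an entry after the final database lock, so if the written analysis has been run, report the revised one beside it and label it as added later.

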2.7.2.5 Time to event analysis for reinfection

Reinfection is defined as appearance of asexual parasites after clearance of initial infection with a genotype different from those parasites present at baseline. Reinfection must be confirmed by PCR analysis.

Incidence rates of reinfection at Days 15, 29 and 43 will be estimated by the Kaplan-Meier method based on the subset of FAS patients who have clearance of initial infection before Day 15.

Time to event (reinfection) will be calculated from the time of first study medication to the date of first event if a patient experiences the event and be censored at the time of last parasite assessment if a patient does not experience the event. Indetermine treatment failures due to missing PCR data will be considered as censored at the time of treatment failure.

2.7.2.6 Pooled efficacy analyses

PK run-in part will not be pooled in the pooled efficacy analysis. The following additional analyses will be performed on pooled Part A and Part B (and pooled PK run-in cohorts, if available):

- For PCR corrected and uncorrected ACPR rates, the treatment differences versus control will be evaluated using a Mantel-Haenszel estimate of the common risk difference stratified by Part (see SAS manual version 13.2 Pages 2681-2682, 2014).
- For PCT and FCT, the difference between each test group and control will be evaluated using a stratified log-rank test (stratified by part).
- In addition, between treatment differences among the following KAF156 and LUM-SDF combinations will be evaluated to support the contribution of individual component for Part A:
 - KAF800 mg/LUM 960 mg-1D vs KAF400 mg/LUM 960 mg-1D
 - KAF200 mg/LUM 480 mg-3D vs KAF400 mg/LUM 480 mg-3D
 - KAF800 mg/LUM 960 mg-1D vs KAF400 mg/LUM 960 mg-2D
 - KAF400 mg/LUM 960 mg-3D vs KAF400 mg/LUM 480 mg-3D

PCR corrected/uncorrected ACPRs at Day 29, PCT, and FCT will be summarized descriptively by the following subgroups

- Age groups as per section 2.3
- Baseline Weight groups as per section 2.3
- Sex (male vs female)
- Region

2.8 Safety analyses

All safety analyses will be performed using the safety set. Safety data for PK run-in cohort will be summarized separately. Part A and Part B will be pooled for selected safety analysis.

2.8.1 Adverse events (AEs)

The number and percent of patients with treatment emergent adverse events will be presented. The treatment emergent adverse events (events started on or after the first dose of study medication or events present prior to the first dose of study medication but increased in severity based on preferred term) will be summarized by primary System Organ Class (SOC) and Preferred Term (PT).

Adverse events will be summarized by presenting, for each treatment group, the number and percentage of patients having at least one AE, having an AE in each primary system organ class and having each individual AE (preferred term). Summaries will also be presented for AEs by severity (Toxicity grade) and for study treatment related AEs. If a patient reported more than one adverse event with the same preferred term, the adverse event with the greatest severity will be presented. If a patient reported more than one adverse event within the same primary system organ class, the patient will be counted only once with the greatest severity at the system organ class level, where applicable.

The MedDRA version used for reporting the adverse events will be described in a footnote.

The most common adverse events reported ($\geq z$ % in any group for each preferred term in the table by SOC and PT) will be presented in the clinical study report by descending frequency according to its incidence in overall group starting from the most common event. Here threshold value z is set to 5 (%) but it may be updated following review of the dry run outputs.

Separate summaries will be provided for deaths, serious adverse events, severe malaria, other significant adverse events leading to treatment discontinuation and adverse events leading to dose adjustment.

Serious adverse events in screening phase will be flagged in data listing due to rare frequency.

Patients who experienced a grade 3 or grade 4 AE will be summarized.

For the legal requirements of ClinicalTrials.gov and EudraCT, two required tables on treatment emergent adverse events which are not serious adverse events with an incidence greater than 5% and on treatment emergent serious adverse events and SAE suspected to be related to study treatment will be provided by system organ class and preferred term on the safety set.

If for a same patient, several consecutive AEs (irrespective of study treatment causality, seriousness and severity) occurred with the same SOC and PT:

- a single occurrence will be counted if there is ≤ 1 day gap between the end date of the preceding AE and the start date of the consecutive AE
- more than one occurrence will be counted if there is > 1 day gap between the end date of the preceding AE and the start date of the consecutive AE

For occurrence, the presence of at least one SAE / SAE suspected to be related to study treatment / non SAE has to be checked in a block e.g., among AE's in a ≤ 1 day gap block, if at least one SAE is occurring, then one occurrence is calculated for that SAE.

Number of deaths resulting from SAEs suspected to be related to study treatment and number of deaths resulting from SAEs irrespective of causality will be provided.

The adverse events and SAEs pooled from Parts A and B will be summarized overall and for the following subgroups.

- Age groups as per section 2.3
- Baseline Weight groups as per section 2.3
- Sex (male vs female)
- Region

Algorithms for date imputations is provided in Appendix 5.

2.8.1.1 Adverse events of special interest / grouping of AEs

The adverse events of special interest are defined in the Case retrieval Sheet (CRS) which is updated for each MEDDRA dictionary. The CRS data are stored in RDCRS SAS dataset corresponding to a subset of eCRS SAS view for which the following filtering criteria are applied

-Drug code = KAF156

-the latest version of MedDRA at the time of final database lock.

-End date is null (this means this is the latest CRS version). Potential risks based on the current CRS are listed in [Table 2-1](#).

The number and percent of patients with these special AEs will be summarized. In addition, listings of related adverse events will be provided.

Newly occurring liver enzyme abnormalities and QTcF abnormalities will be summarized (see [Sections 2.8.2 and 2.8.3.1](#))

Table 2-1 List of safety topics of interest

Safety Topic Of Interest	SOC	Search Criteria Details	MedDRA Code	MedDRA Term	MedDRA Level	MedDRA Qualifier
Gastrointestinal tolerability	Gastrointestinal disorders		20000140	Gastrointestinal nonspecific symptoms and therapeutic procedures (SMQ)	MQ2	BROAD
Bradycardia	Cardiac disorders		90003924	Bradycardia [KAF156] (CMQ)	NMQ1	
Gastrointestinal bleeding and ulceration	Gastrointestinal disorders		90003929	Gastrointestinal bleeding and ulceration [KAF156] (CMQ)	NMQ1	
Renal tubular necrosis	Renal and urinary disorders		90003925	Renal tubular necrosis [KAF156] (CMQ)	NMQ1	
Thyroid hypertrophy and hyperplasia	Endocrine disorders		90003926	Thyroid hypertrophy and hyperplasia [KAF156] (CMQ)	NMQ1	
Hepatotoxicity (GenMed)	Hepatobiliary disorders	ALT/AST > 3 ULN; ALP > 2 ULN; TBL>1.5 ULN; ALP >3 ULN and TBL>2 ULN; ALT/ AST > 3 ULN and TBL>2 ULN; ALT/AST > 3 ULN and TBL >= 2 ULN and ALP <2 ULN'	20000006	Drug related hepatic disorders – comprehensive search (SMQ)	MQ2	BROAD
QTc prolongation	Cardiac disorders	Number of pts with notable QTcF, those with QTcF>500 msec, or increase by >=60 msec over baseline. Sustained ventricular tachycardia lasting 30 sec or more, or ventricular fibrillation	20000001	Torsade de pointes/QT prolongation (SMQ)	MQ1	BROAD

Hematological disorders	Blood and lymphatic system disorders		20000027	Haematopoietic cytopenias (SMQ)	MQ1	BROAD
Antimalarial drug resistance	Infections and infestations		90003928	Anti-malarial drug resistance [KAF156] (CMQ)	NMQ1	
Drug – Drug Interactions	General disorders and administration site conditions		90000024	Interactions (PSUR) [STANDARD] (NMQ)	NMQ1	

